5.3.1.1.7. Virologic Breakthrough

HBV virological breakthrough is defined as having a confirmed on-treatment HBV DNA increase by >1 log₁₀ from nadir level (lowest level reached during treatment) in participants who didn't have on-treatment HBV DNA level below the lower limit of quantification (LLOQ) or a confirmed on-treatment HBV DNA level >200 IU/mL in participants who had on-treatment HBV DNA level below the LLOQ. Confirmed HBV DNA increase/level means that the criterion should be fulfilled at 2 or more consecutive time points or at the last observed on-treatment time point. On-treatment will be defined as the time period in which the participant receives any of the study interventions (including NA).

In addition, participants who experience a virologic breakthrough followed by on-treatment biochemical flare will be evaluated.

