	
HBsAg <100 IU/mL or >1 log₁₀ IU/mL reduction in HBsAg from baseline).
 
 Proportion of participants with HBV DNA levels and/or changes from baseline below/above different cut-offs (eg, <LLOQ of the assay). Proportion of participants with flares (virologic, biochemical, and clinical).

 To evaluate the frequency of virologic breakthrough during study intervention. 	
 Proportion of participants with virologic breakthrough.

 To evaluate the proportion of participants requiring NA re-treatment during follow-up. 	
 Proportion of participants who meet the NA re-treatment criteria.

 To identify baseline and on-treatment markers associated with sustained off-treatment response. 	
 Correlation of baseline characteristics and baseline/on-treatment viral blood markers (such as baseline NA treatment duration, age, and baseline/on-treatment HBsAg levels) with selected off-treatment efficacy variables.

 To evaluate the PK of JNJ-3989 (JNJ-3976 and JNJ-3924), JNJ-6379, and NA, as applicable. 	
 Population PK parameters of JNJ-3989 (JNJ-3976 and JNJ-3924), JNJ-6379, and NA, as applicable.
Exploratory	

 To evaluate the efficacy of NA re-treatment during follow-up. 	
 Proportion of participants with decline in HBV DNA, ALT and/or HBsAg levels after restart of NA treatment during follow-up.

 To explore changes in the severity of liver disease. 	
 Changes in fibrosis (according to Fibroscan liver stiffness measurements) at end-of-study intervention (EOSI) and end of follow-up versus baseline.

 To explore the efficacy in terms of changes in HBV RNA and HBcrAg levels. 	
 Changes from baseline in HBV RNA and HBcrAg levels during study intervention and follow-up.

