5.1. Inclusion Criteria

Each potential participant must satisfy all of the following criteria to be enrolled in the study:

M01/ A01. Male or female participants ≥ 18 years of age (or the legal age of consent in the jurisdiction in which the study is taking place) to ≤ 65 years of age.

M02. Participant must be medically stable based on physical examination, medical history, vital signs, and 12-lead ECG performed at screening. If there are abnormalities, they must be consistent with the underlying illness in the study population. This determination must be recorded in the participant’s source documents and initiated by the investigator.

M03/ A02. Participants must have HBV infection documented by serum HBsAg positivity at screening. In addition, chronicity must be documented by any of the following at least 6 months prior to screening: serum HBsAg positivity, HBeAg or HBV DNA positivity, ALT elevation above ULN without another cause than HBV infection, documented transmission event, liver biopsy with changes consistent with chronic HBV, or should be documented by absence of marker for acute infection such as positive immunoglobulin M (IgM) anti-hepatitis B surface (HBs) and anti-HBc antibodies, which can be tested at screening.

The participants should be virologically suppressed. They should:

- Be HBeAg-negative,
- Be on stable HBV treatment, defined as currently receiving NA treatment (ETV, TDF, or TAF) for at least 24 months prior to screening and having been on the same NA treatment regimen (at the same dose) as used in this study (see Section 6.1) for at least 3 months at the time of screening, AND
- Have serum HBV DNA <60 IU/mL on 2 sequential measurements at least 6 months apart (one of which is at screening), AND
- Have documented ALT values $<2.0 \times$ ULN on 2 sequential measurements at least 6 months apart (one of which is at screening).

M04. Participants must have a body mass index (weight in kg divided by the square of height in meters) between 18.0 and 35.0 kg/m^2 , extremes included.

M05/ Participant must sign a Master ICF (specific for the Master Protocol PLATFORMPAHPB2001) and an ICF specific for this ISA indicating that he or she

A03. understands the purpose of, and procedures required for, the study and is willing to participate in the study.

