6.7. NA Re-treatment Criteria and Monitoring After Stopping of NA

After completing treatment with JNJ-3989, JNJ-6379 (or their matching placebos) and NA at Week 48 (or after premature discontinuation), participants will be monitored closely during the follow-up phase.

After stopping NA treatment, participants should be monitored as follows:

- Regular monitoring visits will be every 4 weeks during the follow-up phase in accordance with the [Schedule of Activities](#).
- A post-treatment HBV DNA value of >20,000 IU/mL should trigger re-testing of ALT/AST, HBV DNA, and total and direct bilirubin within a maximum of 7 days from receipt of the data and further repeats as necessary (ie, weekly until HBV DNA returns to <20,000 IU/mL).
- A post-treatment HBV DNA value of >2,000 IU/mL (but <20,000 IU/mL) should trigger a re-test within 14 days from receipt of the data and further repeats as necessary (ie, every other week until HBV DNA returns to <2,000 IU/mL).
- A post-treatment ALT value of >5x ULN should trigger re-testing of ALT, AST, alkaline phosphatase (ALP), total and direct bilirubin, INR, albumin, and HBV DNA on a weekly basis until ALT and AST levels have returned to <5x ULN.

After stopping NA treatment, participants should restart NA treatment:

- Immediately with signs of decreasing liver function based on laboratory findings (eg, INR, direct bilirubin) or clinical assessment (eg, ascites, hepatic encephalopathy).
- Immediately with an HBV DNA value of >100,000 IU/mL (irrespective of confirmation and/or ALT increase).
- With confirmed post-treatment HBeAg seroreversion (HBeAg positive after it was negative at NA completion).
- With confirmed* post-treatment increases in HBV DNA >2,000 IU/mL and ALT >5x ULN.
- With confirmed* post-treatment increases in HBV DNA >20,000 IU/mL.

*At least 4 weeks apart frequency of visits as described above.

Note: Additional re-testing and/or earlier restarting of NA treatment is at the investigator's discretion, even if the above cut-offs are not yet met.

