2. GENERAL ANALYSIS DEFINITIONS

The SAP will use throughout the document the following definitions:

- Study treatment refers to: JNJ-3989, JNJ-6379, placebo and NA (ETV, TDF, or TAF)
- Study agent refers to: JNJ-3989, JNJ-6379, or placebo
- Study intervention arm refers to:
 - Arm 1: JNJ-3989 (200 mg) + JNJ-6379 (250mg qd) + NA
 - Arm 2: Placebo + Placebo + NA

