5.3.1.3.3. Time to Virologic Breakthrough

Time to HBV virologic breakthrough will be defined as the number of days between the date of first study intervention intake and the date of the first occurrence of virologic breakthrough (i.e. the date of the first virologic breakthrough [the first of the two confirmation visits] - the date of first study intervention intake +1). The participants who withdrew early from the study before experiencing virologic breakthrough or who did not experience virologic breakthrough will be censored at the last available HBV DNA assessment at or before EOT.

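### The on-treatment window for virologic breakthrough does not exclude NA re-treatment, so residual viraemia after an NA restart in follow-up can be counted as breakthrough

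*SAP*

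**What the plan says.** The protocol objective (Section 3) is: "To evaluate the frequency of virologic breakthrough during study intervention". For participants who reached LLOQ on treatment, SAP 5.3.1.1.7 makes the event "a confirmed on-treatment HBV DNA level >200 IU/mL in participants who had on-treatment HBV DNA level below the LLOQ". Confirmation means that "the criterion should be fulfilled at 2 or more consecutive time points or at the last observed on-treatment time point". The window is set by this sentence: "On-treatment will be defined as the time period in which the participant receives any of the study interventions (including NA").

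SAP Section 2 counts NA as study treatment without limiting it to a phase: "Study treatment refers to: JNJ-3989, JNJ-6379, placebo and NA (ETV, TDF, or TAF"). The follow-up schedule in Protocol 1.3.2 also lists NA dispensing under study intervention administration.

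For time to breakthrough (SAP 5.3.1.3.3), participants without an event "will be censored at the last available HBV DNA assessment at or before EOT". SAP 2.1.3 defines EOT as the last post-baseline visit of the double-blind phase.

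Under SAP 5.3.1.1.6, a virologic flare ends when HBV DNA is back to 200 IU/mL or lower (or, in its second derivation, to within 1 log10 of the end-of-treatment value) or when treatment restarts, whichever is first. The same section assesses virologic flares off treatment only and refers on-treatment ones to the breakthrough definition.

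**The concern.** All participants are meant to stop everything, NA included, at Week 48, and some will restart NA because HBV DNA has rebounded. Once NA is restarted they are again receiving a study intervention, so the window reopens. Their flare has ended by rule at the restart date, and what remains of the same rebound falls under the breakthrough rule. Most would satisfy the condition of having been below LLOQ on treatment, because entry required them to "Have serum HBV DNA <60 IU/mL on 2 sequential measurements at least 6 months apart".

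Breakthrough should mean that suppression was lost while on therapy. A rebound off NA that has not yet cleared after restart is a different event. Mixing the two would affect three outputs:

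- the proportion with breakthrough, a listed secondary endpoint;
- the evaluation of breakthrough followed by on-treatment biochemical flare (SAP 5.3.1.1.7);
- the sequencing time point at breakthrough, which SAP 7.1 takes from 5.3.1.1.7. SAP 7.5.1 plans separate tables for breakthrough, flare and re-treatment, and one rebound could enter all three.

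**Working it through.** The plan gives no figure to reproduce. The check applies the SAP rule as written to a participant who restarts NA at the thresholds in Protocol 6.7.

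**Inputs**
- Breakthrough limit: 200 IU/mL (SAP 5.3.1.1.7).
- HBV DNA restart thresholds (Protocol 6.7): above 2,000 IU/mL with ALT above 5x ULN, confirmed; "With confirmed* post-treatment increases in HBV DNA >20,000 IU/mL"; above 100,000 IU/mL at once. These are 2,000/200 = 10, 20,000/200 = 100 and 100,000/200 = 500 times the limit.
- Rate of fall (assumption): log-linear at 3.5/12 = 0.292 log10 per week. Protocol 2.2.1 reports a mean fall of more than 3.5 log10 at Week 12 on 75 mg JNJ-6379 monotherapy and calls the fall with JNJ-6379 or placebo plus NA similar. Range used: 0.195 (0.67 times) to 0.583 (2 times).
- Sampling: 4-weekly, the regular interval after stopping NA.

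**Formulas**
- Weeks to reach 200 = log10(start/200) / rate. At 0.292: 1.00/0.292 = 3.4, 2.00/0.292 = 6.9 and 2.70/0.292 = 9.3 weeks.
- Value at week w = start x 10^(-rate x w). From 100,000 at Week 4: 100,000 x 10^(-1.167) = about 6,800.

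| Restart at (IU/mL) | Rate | Weeks to 200 | Week 4 | Week 8 | Two consecutive values >200? |
|---|---|---|---|---|---|
| 2,000 | 0.195 | 5.1 | 331 | 55 | Conditional |
| 2,000 | 0.292 | 3.4 | 136 | 9 | No |
| 2,000 | 0.583 | 1.7 | 9 | 0 | No |
| 20,000 | 0.195 | 10.2 | 3,307 | 547 | Yes |
| 20,000 | 0.292 | 6.9 | 1,363 | 93 | Conditional |
| 20,000 | 0.583 | 3.4 | 93 | 0 | No |
| 100,000 | 0.195 | 13.8 | 16,532 | 2,733 | Yes |
| 100,000 | 0.292 | 9.3 | 6,813 | 464 | Yes |
| 100,000 | 0.583 | 4.6 | 464 | 2 | Conditional |

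Conditional means confirmed only if the restart-day sample counts as on-treatment or sampling is denser (2-weekly suffices in these rows). The thresholds are lower bounds for protocol-triggered restarts, although investigators may also restart NA earlier at their discretion.

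The alternative confirmation route needs only one value above 200 IU/mL at the last observed on-treatment time point. A restart shortly before an analysis cut-off or Week 96 could qualify that way from any of these levels.

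**Scale.** On planned arm sizes, each misclassified participant adds 1/80 = 1.25 percentage points in the investigational arm or 1/40 = 2.5 points in the control arm.

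**The case against.** The strongest reply is that the surrounding text shows what was meant. The objective speaks of the intervention period, and Protocol 10.1 describes the study intervention phase as 48 weeks. Protocol 9.4.1.2 contrasts breakthrough on treatment with responses in follow-up. Protocol 7.1 lists confirmed breakthrough among the reasons for stopping the investigational agents before Week 48. SAP Section 5 analyses efficacy by phase, and the double-blind phase in SAP 2.1.1 does not extend with NA, so events after restart would appear under follow-up. SAP 5.3.2.1.3 reports biochemical flares after NA re-treatment separately.

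This is good evidence of intent, but none of it changes the derivation. No passage excludes re-treatment time from this endpoint, and reporting by phase does not alter the sequencing key.

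Three stronger readings are tempting, and the documents do not support them:

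- A reader might infer that everyone who restarts NA becomes a breakthrough. Restart alone does not qualify; a confirmed value above 200 IU/mL while on NA is needed.
- A reader might infer that 5.3.1.3.3 flatly contradicts 5.3.1.1.7. It only censors participants without an event at or before EOT and does not restrict when an event may occur. The two fit poorly together, but that is not a contradiction.
- A reader might infer a count of false cases, or that they would outnumber true ones. The protocol does report no breakthrough in the earlier JNJ-6379/placebo plus NA arms, but those are interim data from another study, and no restart rate is given here.

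It also stands that the consequences are limited. Breakthrough is summarised by arm and is not among the endpoints listed for Mantel-Haenszel comparison in SAP 5.3.2.1. The primary endpoint is untouched, because NA re-treatment between Weeks 48 and 72 is already non-response.

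**Conclusion.** The point holds as a defect in the definition. Followed literally, the rule can class residual viraemia after an NA restart as breakthrough and carry it into the flare and sequencing outputs. Two programmers could derive different breakthrough rates from the same data.

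How many restarters qualify depends on the HBV DNA level at restart, the rate of fall, the sampling interval and whether the restart-day value counts. Under the central assumption, restarts from 100,000 IU/mL are caught, those from 20,000 IU/mL are conditional, and those from 2,000 IU/mL are not caught unless the last-time-point rule applies. The rate of fall is an assumption borrowed from another study. The overall number affected cannot be derived from the documents. The correction should be made, but it bears on a secondary endpoint and the resistance tables, not on the primary conclusion.

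**What to change.** Replace the last sentence of the definition in SAP 5.3.1.1.7 with wording to this effect: on-treatment for this endpoint runs from first intake to the first stop of all study interventions including NA, and excludes any period after NA restart. The last observed on-treatment time point is then the last one in that window.

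Add that participants who do not stop NA at Week 48 (Protocol 6.6) remain on-treatment while NA is uninterrupted, with events after EOT shown under the follow-up phase. Cutting the window at the last double-blind dose would be simpler, but it would discard genuine loss of suppression in this group.

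In 5.3.1.3.3, apply the same window to events and censoring: count events only within it, and censor the rest at the last HBV DNA assessment within it.

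The cost is two or three sentences and one derived date. No new data or output is needed, because HBV DNA after restart is already covered in Protocol 9.4.1.2 and SAP 5.3.1.1.5 and 5.4.1.2.1.

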5.3.1.1.8. NA Re-Treatment Criteria During Follow-Up

Participants who actually re-started NA treatment during the follow-up phase will be identified based on the 'Study Drug Administration for ETV, TDF or TAF' CRF page.

Participants who meet the NA re-treatment criteria will be identified based on the CRF page of 'NA Re-treatment Criteria Assessment'. Each sub-criteria will also be evaluated.

5.3.1.1.9. ALT Normalization

ALT elevation at baseline is defined as $ALT \geq ULN$. A participant with ALT elevation at baseline achieves ALT normalization if his/her ALT value post-baseline is $< ULN$ at any given time point.

Participants who achieve ALT normalization on treatment and off treatment but without restarting NA treatment will be evaluated over time.

Participants who were re-treated with NA and who have $ALT \geq ULN$ before NA re-treatment and reach ALT normalization after NA re-treatment during follow-up will be evaluated.

Additionally, for those participants who restarted NA treatment during the follow-up, the participants who reach $ALT < ULN$ and who have ALT less than their nadir value during the study will be evaluated.

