IWRS	interactive web response system
LLN	lower limit of normal
LLOQ	lower limit of quantification
MoA	mode of action
MRI	magnetic resonance imaging
NA	nucleos(t)ide analog
NOAEL	no observed adverse effect level
PBMC	peripheral blood mononuclear cell
PD	pharmacodynamic(s)
pgRNA	pre-genomic ribonucleic acid
PK	pharmacokinetic(s)
PRO	patient-reported outcome(s)
qd	once daily
QTcF	QT interval corrected for heart rate according to Fridericia's formula
RBC	red blood cell
RNA	ribonucleic acid
RNAi	ribonucleic acid interference
SAE	serious adverse event
SAP	Statistical Analysis Plan
SBP	systolic blood pressure
SD	standard deviation
siRNA	small interfering ribonucleic acid
$t_{1/2\text{term}}$	terminal half-life
TAF	tenofovir alafenamide
t_{max}	time to reach C_{max}
TDF	tenofovir disoproxil fumarate
TNF	tumor necrosis factor
ULN	upper limit of normal
VAS	Visual Analog Scale
WBC	white blood cell

Definitions of Terms

ALT/AST nadir	Lowest ALT/AST value during study participation
End-of-study intervention (EOSI)	Time of the last administration of study intervention
HBsAg seroclearance	HBsAg negativity based on the assay used
HBsAg seroconversion	HBsAg negativity and anti-HBs antibody positivity
Intervention cohort	Cohorts of adult participants with chronic hepatitis B virus infection who receive a

	specific study intervention within this Platform study, and in whom the efficacy and safety of that intervention is evaluated
Study intervention	JNJ-73763989 or placebo, JNJ-56136379 or placebo, and NA (either ETV, TDF, or TAF)
Study intervention phase	48-week phase from randomization to last administration of study intervention
Virologic breakthrough	Confirmed on-treatment HBV DNA increase by $>1 \log_{10}$ IU/mL from nadir or confirmed on-treatment HBV DNA level >200 IU/mL in participants who had HBV DNA level $<\text{LLOQ}$ of the HBV DNA assay

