5.3.1.1.5. HBsAg and HBV DNA cut-offs

The cut-offs for HBsAg level are as follows:

- <1000 IU/mL
- <100 IU/mL
- <10 IU/mL
- <1 IU/mL
- <0.05 IU/mL

The cut-offs for HBsAg change from baseline are as follows:

- decrease by $\geq 0.3 \log_{10}$ IU/mL
- decrease by $\geq 0.5 \log_{10}$ IU/mL
- decrease by $\geq 1 \log_{10}$ IU/mL
- decrease by $\geq 2 \log_{10}$ IU/mL
- decrease by $\geq 3 \log_{10}$ IU/mL
- decrease by $\geq 4 \log_{10}$ IU/mL

The cut-offs for HBV DNA are as follows:

- <LLOQ
- <LLOQ TND
- <LLOQ TD
- <60 IU/mL
- <200 IU/mL
- <2000 IU/mL
- <20000 IU/mL
- <100000 IU/mL

HBV DNA change from time of NA re-start

- decrease by $\geq 1 \log_{10}$ IU/mL
- decrease by $\geq 2 \log_{10}$ IU/mL
- decrease by $\geq 3 \log_{10}$ IU/mL
- decrease by $\geq 4 \log_{10}$ IU/mL
- decrease by $\geq 5 \log_{10}$ IU/mL

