5.3.1.1.6. Flares

The criteria based on blood markers/lab tests for each of the flare types are defined as below.

a) Virologic flare is defined as follows:

Derivation 1. This derivation of virologic flare will be assessed only for those participants who are off-treatment and had HBV DNA<LLOQ at the last observed point on all study treatments.

The start date of a virologic flare is defined as the first date of two consecutive visits with HBV DNA > 200 IU/mL. The end date of the same virologic flare is defined as the first date when HBV DNA value returns to ≤ 200 IU/mL or the date of treatment restart, whichever comes first. Each virologic flare will be categorized based on the confirmed (i.e., two consecutive values) peak HBV DNA above any of the four thresholds within the start and end date of that flare as follows: 100,000 IU/mL, 20,000 IU/mL, 2,000 IU/mL and 200 IU/mL.

Derivation 2. This derivation of virologic flare will be assessed only for those participants who are off-treatment and had HBV DNA \geq LLOQ at the last observed point on all study treatments.

The start date of a virologic flare is defined as the first date of two consecutive visits with HBV DNA \log_{10} increase from end of treatment $> 1 \log_{10}$. The end date of the same virologic flare is defined as the first date when HBV DNA \log_{10} increase from end of treatment returns to $\leq 1 \log_{10}$ or the date of treatment restart, whichever comes first. Each virologic flare will be categorized based on the confirmed (i.e., two consecutive values) peak HBV DNA above any of the three thresholds within the start and end date of that flare as follows: 1 \log_{10} , 2 \log_{10} and 3 \log_{10} .

- 1 (Yes) = confirmed** HBV DNA > peak threshold.
- 0 (No) = at least one off-treatment HBV DNA measurement available and not meeting the criteria of confirmed HBV DNA > peak threshold.
- 2 (Not applicable) = no off-treatment HBV DNA quantitative measurements available.

b) Biochemical flare is defined as follows:

- 1 (Yes) = confirmed** ALT and/or AST $\geq 3x$ ULN and $\geq 3x$ nadir (ie, lowest value observed up to the start of the flare)
- 0 (No) = otherwise

The start date of a biochemical flare is defined as the first date of two consecutive visits with ALT and/or AST $\geq 3x$ ULN and $\geq 3x$ nadir. The end date of the same biochemical flare is defined as the first date when there is a 50% reduction from the peak ALT and/or AST level & $< 3x$ ULN.

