5.4.1.2.1. Decline in HBsAg and HBV DNA Levels

Participants achieving the maximum decline (change from peak level in follow-up to the lowest level achieved during the remainder of follow-up) in the magnitude of the cut-offs as described in Section 5.3.1.1.5 will be evaluated by intervention arm and over time in the follow-up phase only for those participants who restarted NA treatment during the follow-up.

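### Two SAP summaries of response to NA re-treatment are not tied to the restart date: HBsAg and HBV DNA decline is counted from the follow-up peak, and an additional ALT criterion cannot be met as worded

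*SAP*

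**What the plan says.** The protocol's exploratory endpoint for NA re-treatment (Section 3, repeated in SAP 1.1) is the proportion of participants with "decline in HBV DNA, ALT and/or HBsAg levels after restart of NA treatment during follow-up".

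Four SAP rules bear on it:

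- **SAP 5.4.1.2.1** covers HBsAg and HBV DNA. It is limited to "participants who restarted NA treatment during the follow-up" and defines decline as "change from peak level in follow-up to the lowest level achieved during the remainder of follow-up". It borrows its magnitudes from 5.3.1.1.5.
- **SAP 5.3.1.1.5** lists HBV DNA decreases of 1 to 5 log10 under the label "HBV DNA change from time of NA re-start". Its HBsAg decreases, 0.3 to 4 log10, are changes from baseline.
- **SAP 5.3.1.1.9, first re-treatment rule,** takes participants with ALT at or above ULN before re-treatment who "reach ALT normalization after NA re-treatment during follow-up will be evaluated".
- **SAP 5.3.1.1.9, additional rule,** takes restarters with ALT below ULN "who have ALT less than their nadir value during the study will be evaluated".

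Protocol Appendix 1 defines the ALT/AST nadir as "Lowest ALT/AST value during study participation". For flares, SAP 5.3.1.1.6 limits it in time: "lowest value observed up to the start of the flare".

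**The concern.** In 5.4.1.2.1, restarting NA only selects who is analysed. Neither the peak nor the fall has to come after the restart date. A participant whose marker peaks, falls untreated and then restarts NA has the whole fall counted as response to NA. For HBV DNA this conflicts with the restart-anchored list in 5.3.1.1.5. For HBsAg the SAP has no restart-anchored rule at all.

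Taking the highest value and then the lowest later one also selects extremes, so measurement noise alone yields an apparent decline.

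The additional ALT rule asks for a value strictly below a minimum which, on the protocol's definition, already includes that value.

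At stake is the exploratory objective of evaluating the efficacy of NA re-treatment. The HBsAg summary would be biased upward, and one ALT summary would be empty in both arms or would depend on how a programmer guesses the nadir window.

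**Working it through.** **Plan's own figure.** The documents give none for these summaries. The only design figure is power above 91% for the primary endpoint (80 v 40, 25% v 5%, one-sided 0.05). Exact enumeration of the unstratified Mantel-Haenszel test gives 91.7%, which agrees. Nothing below changes it.

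**Step 1: credit for falls before restart.** Let P be the follow-up peak, R the last value on or before restart, and L the lowest value after the peak. When the peak precedes restart and L follows it:

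SAP decline = P − L = (P − R) + (R − L).

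Only R − L is decline after restart. Take an invented HBV DNA series in log10 IU/mL: 0.7, 2.5, 4.8, 5.6, 4.4, 4.2 (restart), 3.9, 3.6.

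- From peak: 5.6 − 3.6 = 2.0
- From restart: 4.2 − 3.6 = 0.6
- Credited but untreated: 5.6 − 4.2 = 1.4

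The 1 log10 cut-off is passed only when counting from the peak. The series shows the arithmetic, not a typical course: 5.6 log10 is about 398,000 IU/mL, above the 100,000 IU/mL at which Protocol 6.7 calls for immediate restart.

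The restart thresholds in Protocol 6.7 show what P − R could be for a participant who never exceeded 100,000 IU/mL (5.0 log10):

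- restart on confirmed HBV DNA above 20,000 (4.3 log10): up to 5.0 − 4.3 = 0.7 log10;
- restart on confirmed HBV DNA above 2,000 (3.3 log10) with raised ALT: up to 5.0 − 3.3 = 1.7 log10;
- restart for liver function, HBeAg seroreversion or investigator discretion: no HBV DNA floor applies.

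These are limits, not expected values. HBsAg plays no part in the restart criteria, so nothing ties its peak to the restart date.

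**Step 2: false decline from selecting extremes.** Simulation of 200,000 participants with independent normal values and no trend; decline is the peak minus the lowest value at or after it. The SDs are assumptions, because the documents give none. Thirteen is the number of scheduled follow-up visits when all treatment is stopped (Protocol 1.3.2).

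| Visit SD (log10) | Values | ≥0.3 log10 | ≥0.5 log10 | ≥1 log10 |
|---|---|---|---|---|
| 0.08 | 5 / 9 / 13 | 3% / 9% / 16% | 0% / 0% / 0% | 0% |
| 0.10 | 5 / 9 / 13 | 11–12% / 27% / 41–42% | 0.2% / 0.6–0.7% / 1.3% | 0% |
| 0.15 | 5 / 9 / 13 | 37% / 63% / 77% | 7% / 18% / 29% | 0% |

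For comparison, one fixed reference value against one later value exceeds 0.3 log10 with probability 1 − Φ(0.3 / (SD × √2)). That is 0.4%, 1.7% and 7.9% at SD 0.08, 0.10 and 0.15.

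**Step 3: the ALT nadir.** Let S be all of a participant's ALT values in the study and x any value after restart. Since x belongs to S, x ≥ min(S), so x < min(S) is never true and the count is 0 in both arms. If the nadir covers only values before restart, the rule can be met: with a pre-restart nadir of 24 U/L, a later 22 U/L qualifies.

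**The case against.** The strongest defence is that the SAP does measure re-treatment elsewhere, and this stands. The first re-treatment rule in 5.3.1.1.9 is a valid before/after comparison, and 5.3.1.1.5 has HBV DNA change from restart. Protocol 9.4.1.2 also compares the arms on HBV DNA <LLOQ and/or ALT normalization after restart. A reader might infer that no SAP criterion measures re-treatment, or that the objective gets only a structural zero for ALT. The documents do not support either inference.

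Second, the nadir could mean lowest to date. The protocol uses the same phrase as a live trigger for a confirmatory visit (8.3.6.3), where it can only work that way, and the flare definition is time-limited. So the zero follows from the literal reading, not the only possible one. But the SAP states a window in its other nadir definitions, and the words in 5.3.1.1.9 point to the whole study.

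Third, the noise result is narrow. It matters mainly at the smallest HBsAg cut-off and vanishes at 1 log10, where the HBV DNA cut-offs begin. It therefore does not show a noise-inflated HBV DNA rate. Thirteen values also overstates the data on many restarters, because stable ones move to visits at least every 12 weeks.

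Fourth, several restart criteria are triggered by high HBV DNA, so peak and restart may often be close. If the peak is at or after restart, the decline is wholly post-restart. This limits the HBV DNA problem but does not remove it.

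Two further inferences fail. The HBsAg change-from-baseline cut-offs serve a separate secondary endpoint, so they are not a third anchor for re-treatment; 5.4.1.2.1 borrows only their magnitudes. A bias that differs by arm is conceivable, for example if HBsAg rebounds late in the active arm, but the documents give no figure for it.

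**Conclusion.** The point holds for two summaries and is minor. The decline rule in 5.4.1.2.1 does not match its endpoint: it can credit untreated falls to NA, it conflicts with 5.3.1.1.5 for HBV DNA, and it leaves HBsAg without a restart reference. The size of the pre-restart credit, and any difference between arms, cannot be quantified from the documents. The false-decline rates rest on assumed SDs, independent visits and no true change.

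The additional ALT rule in 5.3.1.1.9 cannot be met when read with the protocol's definition of nadir. It works only if the window ends before restart, which the text does not say. Both summaries are descriptive and confined to restarters. The primary endpoint is untouched.

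**What to change.** **SAP 5.4.1.2.1.** Define the reference as the last value on or before the NA restart date, for both HBsAg and HBV DNA. Report change from it at fixed times after restart and at the last visit, using the 5.3.1.1.5 magnitudes. Align the two sections so that HBV DNA has one starting point and HBsAg has the same one.

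**SAP 5.3.1.1.9.** Define the nadir in the additional rule as the lowest ALT observed up to NA restart. Leave the before/after normalization rule as it is.

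**Cost.** Two SAP sentences, the alignment of 5.3.1.1.5 and a derivation change; no new data. Reported declines will be somewhat smaller. Two weaknesses remain:

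- The value at restart may itself have been selected for being high, so some regression to the mean persists for HBV DNA.
- The lowest of several post-restart ALT values can fall below the earlier nadir by chance. With 14 values before and 6 after restart and no trend, the overall minimum falls in the later group with probability 6/20 = 30%. The ALT summary should therefore be read descriptively.
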